1.3.2 Summary of Clinical Studies

The efficacy of Dysport® as a treatment of UI related to NDO has been reported in several published studies [10, 11, 12, 13, 14, 15, 16]. Administered doses were 500 U, 750 U, or 1000 U in the detrusor muscle. Positive efficacy data were reported with all the doses for UI, urodynamic parameters, patient satisfaction and patient QoL. A possible dose effect was suggested in some studies, in particular, lower efficacy was observed with Dysport® 500 U compared with 750 U for clinical and urodynamic data in a randomised trial of 77 patients with NDO [15]. All doses were well tolerated with the only adverse event (AE) of note being transient muscular weakness occurring in 14 out of 427 patients (3.3%) after treatment with 1000 U (10 patients) and 750 U (4 patients) of Dysport®. All of these events resolved spontaneously within 4 to 8 weeks [12, 13, 14, 15].

An exploratory phase IIa placebo controlled study in 47 adult patients with NDO secondary to SCI or MS has been conducted (Ipsen Study Y-52-52120-155) [17]. The study compared a total dose of 750 U of Dysport® with placebo, divided as either 15 or 30 intradetrusor injection points (all at a volume of 0.5 mL per injection point). A dose of 750 U Dysport® showed a decrease in daily incontinence frequency by 76% (15 injection points) and 88% (30 injection points) at the 12-week timepoint. Improvements were observed in clinical and urodynamic variables, and patient QoL. No unexpected safety events occurred, although three muscular weakness episodes were reported as serious adverse events (SAEs) in 3 subjects with SCI treated at the higher concentration (750 U divided in 15 injection points), all of whom came from a single research site. The findings may therefore be attributed to either a site effect or a drug-concentration effect (double the drug concentration per injection site compared to the 30-injection points group). The study was not designed for a formal comparison between these two administration modes, but the benefit/risk profile appeared to be more favourable at the dose of 750 U in 30 injection points compared to 750 U in 15 injection points. The administration at 30 injection points remains the current gold standard for injecting BTX-A in the detrusor in NDO patients, and will be utilised in this phase III study.

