4 SELECTION AND WITHDRAWAL OF SUBJECTS

4.1 Inclusion Criteria

The following inclusion criteria will be assessed at the beginning of the Screening process:

- 1) Written informed consent prior to any study related procedure.
- 2) Male or female, aged 18 to 80 years inclusive.
- 3) UI for at least 3 months prior to Screening as a result of NDO due to SCI or MS.
- 4) Subjects with SCI must have a stable neurological injury at T1 level or below which occurred at least 6 months prior to Screening.

OR

Subjects with MS must be clinically stable in the investigator's opinion, with no exacerbation (relapse) of MS for at least 3 months prior to Screening.

- 5) Subjects must have an inadequate response after at least 4 weeks of oral medications used in the treatment of NDO (e.g. anticholinergics, beta-3 agonists) and/or have intolerable side-effects.

- 6) CCI [REDACTED]

[REDACTED]

- 8) Routinely performing CIC to ensure adequate bladder emptying CCI [REDACTED]

[REDACTED]

- 10) Female subjects of childbearing potential must have a negative pregnancy test result and be willing to use reliable contraceptive measures throughout study participation.

Reliable forms of contraception include but are not limited to:

- hormonal contraceptives (e.g. oral, patch, injection)
- double barrier (e.g. male condom plus spermicide, or female diaphragm plus spermicide)
- intrauterine device
- male partner has had a vasectomy
- total abstinence from intercourse with male partners (periodic abstinence is not acceptable).

Female subjects meeting any of the following criteria are not considered to be of childbearing potential:

- postmenopausal (≥ 47 years of age and amenorrhoeic for at least 12 consecutive months)
- have been sterilised surgically (e.g. bilateral tubal ligation)
- have had a hysterectomy
- have had a bilateral oophorectomy.

- 11) Documented urinary tract ultrasound is available in the 6 months prior to Screening, confirming that no medical issues exist that would preclude entry to the study (e.g. bladder stones or unexplained renal mass).
 - If not performed in the 6 months prior to Screening or results are not available, then a urinary tract ultrasound must be conducted during Screening.

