9.4.7 Safety Evaluation

All safety data will be included in the subject data listings. Analyses and summary tables will be based upon the safety population.

All AEs will be coded according to the Medical Dictionary for Regulatory Activities (MedDRA) (current version at the time of database lock), and will be classified by MedDRA preferred term and system organ class. AE listings will be presented by subject, system organ class and preferred term.

Incidence of all reported AEs/treatment emergent AEs, AESIs, and SAEs will be tabulated by treatment group (600 U, 800 U, placebo for Treatment 1 and 600 U, 800 U for subsequent treatment(s)) and overall. In addition, summary tables will be presented by maximum intensity, drug relationship and AEs associated with premature withdrawal of IMP.

A treatment emergent AE is defined as any AE that occurs during the active phase of the study if:

- It was not present prior to receiving the first dose of IMP; or
- It was present prior to receiving the first dose of IMP but the intensity increased at any point in the study following the first dose of IMP.

Concomitant medication will be coded by using World Health Organisation Drug Dictionary (WHODRUG; current version at the time of database lock) and will be summarised by treatment group (600 U, 800 U, placebo for Treatment 1 and 600 U, 800 U for subsequent treatment(s)) and overall, with the number and percentage of subjects receiving concomitant medication by drug class and preferred drug name.

Summary statistics (mean, median, standard deviation, standard error mean, and range as appropriate) by treatment group and overall will be presented for vital signs, laboratory safety tests, laboratory urinalysis/microscopy etc. at each assessment with change from Baseline. For laboratory safety data, abnormal values will be flagged in the data listings and a list of clinically significant abnormal values will be presented. Shift tables from Baseline of the number and percentage of subjects with low, normal or high values and normal or abnormal examinations will be presented by treatment group (600 U, 800 U, placebo for Treatment 1 and 600 U, 800 U for subsequent treatment(s)).

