All TEAEs identified using the search strategy described above will be medically evaluated during the study, before the database lock and unblinding, by the sponsor to identify events which could possibly represent ‘remote spread of effect of toxin’, or which are suggestive of ‘hypersensitivity reactions’ due to study treatment administration. Cases will be excluded if they are confounded by presence of alternative clinical etiologies (medical history, concomitant medication or diagnosis which could account for the symptoms); if they are considered to be local effects instead of distant spread as judged by the site of injection; the time period between the last study treatment administration and event onset is not in accordance with the expected mechanism of action; or due to insufficient information/evidence to make an assessment.

In the TFLs, only the final list of AESIs confirmed by the sponsor as “a possible remote spread event” or “hypersensitivity reactions” will be taken into account.

All AEs (with TEAEs flagged) reported during the study will be presented in a listing which will be sorted by treatment group in the respective assigned treatment cycle for that AE, subject ID, AE start date and time, primary system organ class (SOC), preferred term (PT), and verbatim text. The treatment cycle where the TEAE onset or intensity increased will be presented in the listing as well. Separate listings of all TEAEs, serious TEAEs, IMP-related TEAEs, TEAE of special interest, other protocol defined TEAEs, TEAEs leading to early withdrawal and TEAEs leading to death reported during the study will also be presented.

Overview tables will be produced for DBPC Cycle, Dysport Cycles and overall for the number and percentage of subjects with at least one of the following TEAEs, where subjects with more than one TEAE in a particular category are counted only once in that category. The number of TEAE occurrences will be provided as well. Note that for TEAEs that could only occur in the MS population (e.g. MS exacerbation), the denominator for the percentage calculation will relate to the number of MS patients; these TEAEs will be identified in the tables.

- any TEAE
 - intensity of TEAE (mild, moderate, severe)
 - Any IMP related TEAE
 - Any TEAE leading to withdrawal
- any serious TEAE
 - any IMP related serious TEAE
 - any serious TEAE leading to withdrawal
- any TEAE of special interest by type of AESI
 - any AESI leading to withdrawal
 - any serious AESI

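### The SAP drops remote-spread candidates from every AESI output when medical history could explain them, with no visible exception for the SCI or MS that all subjects have, so the grouped count may be too low

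*SAP*

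**What the plan says.** SAP 7.7.1 identifies candidate AESIs by a MedDRA term search (list in Appendix VI). Candidates "will be medically evaluated during the study, before the database lock and unblinding, by the sponsor". The rule for the aetiology ground is "Cases will be excluded if they are confounded by presence of alternative clinical etiologies (medical history, concomitant medication or diagnosis", and it is enough that one of these might explain the event. Local effect, implausible timing and insufficient information are separate grounds, and any one of them suffices. The section then limits the outputs: "In the TFLs, only the final list of AESIs confirmed by the sponsor" are used.

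Protocol 4.1, criterion 3, requires "UI for at least 3 months prior to Screening as a result of NDO due to SCI or MS". Criterion 4 requires the SCI to be stable and at least 6 months old, or the MS to be clinically stable with no relapse for 3 months. SAP 7.4.2 handles SCI and MS history as medical history.

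Protocol 8.1.2.11 defines AESIs as AEs suggesting possible remote spread or hypersensitivity. Those AESIs then undergo further sponsor analysis, in which alternate aetiology is one variable to consider alongside injection location and timing. Protocol 9.4.7 states "Incidence of all reported AEs/treatment emergent AEs, AESIs, and SAEs will be tabulated by treatment group". SAP section 8 lists no changes in planned analyses.

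**The concern.** In the protocol, an event is an AESI because it suggests spread, and plausibility is examined afterwards. In the SAP, whether an event is reported as an AESI depends on the outcome of that examination, and the threshold is low: the history need only be capable of explaining the symptoms. Weakness is where this matters most. Protocol 1.4 names excessive muscle weakness among possible remote-spread effects, and protocol 1.3.2 singles out transient muscular weakness as the one notable AE in published NDO use. SCI and MS are both neurological diseases that a reviewer could regard as an explanation for weakness.

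A placebo-controlled period lets the placebo arm show how much weakness comes from the underlying disease. Removing disease-compatible cases one at a time before tabulation takes out true toxin events together with background ones. At stake is the one planned table that answers the remote-spread question as a group, by dose, in a trial whose protocol (1.5) expects the two doses to be distinguished on the balance of efficacy and safety.

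**Working it through.** **Inputs.** Protocol 1.3.2: muscular weakness in 14 of 427 patients, 10 at 1000 U and 4 at 750 U. Protocol 3.3.1: 110 subjects per Dysport arm at Treatment 1, 220 in total. Share of cases excluded, q: not given, so the whole range 0 to 100% is shown.

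**Plan's own figure.** 10 + 4 = 14, and 14/427 = 0.0328, which reproduces the stated 3.3%.

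**Effect of exclusion.** Treat each candidate as excluded with probability q. The reported rate is p(1 − q), the expected count is n·p(1 − q), and the chance of no reported case is [1 − p(1 − q)]^n. With p = 0.0328:

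| Share excluded | Expected per arm (n = 110) | Chance of none, one arm | Expected, both arms (n = 220) | Chance of none, both arms |
|---|---|---|---|---|
| 0% | 3.6 | 2.6% | 7.2 | 0.1% |
| 25% | 2.7 | 6.5% | 5.4 | 0.4% |
| 50% | 1.8 | 16.2% | 3.6 | 2.6% |
| 75% | 0.9 | 40.4% | 1.8 | 16.4% |
| 100% | 0 | 100% | 0 | 100% |

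For example, at q = 50% in one arm: 0.0328 × 0.5 = 0.0164; 110 × 0.0164 = 1.8; (1 − 0.0164)^110 = 0.162.

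The result depends only on the product p(1 − q). A true rate of half 3.28% with no exclusions gives the same 1.8 cases and 16% as the full rate with half excluded. A confirmed-only table cannot tell these two situations apart.

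**Effect on the comparison.** If the same share q is removed in each arm, the risk difference (p_D − p_P) becomes (1 − q)(p_D − p_P), while the ratio p_D/p_P is unchanged. The absolute difference shrinks and the counts behind the ratio become sparser.

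**Whether another planned output gives the grouped count.** SAP 7.7.1 tabulates all TEAEs by SOC and PT for the DBPC Cycle, the first 12 weeks and each Dysport Cycle. Excluded events stay there, but spread-compatible terms sit in separate PT rows. Subject counts cannot be added across rows, because one subject may appear in several. No table of all search-identified events is described.

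**The case against.** The strongest reply is that the rule calls for case-by-case medical judgement and does not apply a label. A TEAE is by definition new or worsened after first dosing, and eligibility requires stable neurological disease. A fixed prior deficit does not by itself explain fresh weakness. This stands. A reader might infer that the exclusion ground is met for every subject and that the AESI table must come out empty; the documents do not support that. They show only that the wording permits exclusion on this ground and that nothing visible restrains it.

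Second, review takes place before unblinding, so cases cannot knowingly be removed by arm. This also stands. A reader might infer that the relative comparison is tilted towards Dysport; with equal shares removed it is not. The loss is in the count and the absolute difference.

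Third, muscular weakness by arm is already reported in the PT tables, including the 12-week window, a summary by aetiology, and the serious and IMP-related tables where the event qualifies. Safety is descriptive, so no test rests on the AESI table. This limits the harm but does not supply the grouped count.

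Fourth, the 14 events occurred at 750 U and 1000 U, the protocol does not split the 427 by dose, and 600 U is below both. In phase IIa, "three muscular weakness episodes were reported as serious adverse events (SAEs) in 3 subjects with SCI", but all came from one site in the 15-injection-point group, and the protocol suggests a site or concentration effect. They do not establish a rate for this trial, which uses 30 points.

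Finally, the text of protocol 8.1.2.9 and 8.1.2.10 (neurological AEs and suspected relapse in MS) is redacted and Appendix VI was not available. Special handling for MS may exist, and the listing of the muscular weakness term cannot be checked. Those two headings concern MS and would not obviously cover SCI.

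**Conclusion.** The point holds as a risk of under-counting and lost sensitivity in the grouped remote-spread outputs. SAP 7.7.1 turns a protocol consideration into a mandatory exclusion, makes no visible exception for the disease that qualifies every subject, and plans no table of what was set aside.

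The size is illustrative: about 3.6 expected muscular weakness cases per arm, with the chance of none rising from 2.6% to 16% or 40% when half or three quarters are excluded. This assumes that the 3.3% rate carries over to 600 U and 800 U and that every such case is caught by the search. The share excluded could be anything from 0 to 100%. With all 220 subjects and no exclusions, a zero count would be very unlikely (about 0.1%), but that describes the absence of the rule and does not measure its effect. It would also go too far to call muscular weakness the main known harm: the protocol describes remote-spread events as very rare (1.4) and raises UTI risk as well (1.7).

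**What to change.** 1. In the AESI tables for the DBPC Cycle, the 12-week window and each Dysport Cycle, show by arm: all TEAEs identified by the Appendix VI search before review; the sponsor-confirmed subset; and those set aside, with the ground for exclusion. Count subjects once per row.
2. Reconcile the exclusion wording in SAP 7.7.1 with protocol 8.1.2.11, so that it is clear whether pre-existing stable SCI or MS alone counts as an excluding alternative aetiology. That medical decision belongs to the sponsor; the request is that it be stated before unblinding and agree across the documents. Record any departure from the protocol in SAP section 8.

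The cost is a short SAP revision and one more group of rows in tables already planned, provided the review records its decision and reason for each case. The unreviewed row will contain background events, which the placebo column puts in context for the DBPC Cycle and the 12-week window. The Dysport Cycles have no concurrent placebo, so there the row should be read beside the confirmed one.

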The effects of Dysport® and all BTX products may spread from the area of injection to produce symptoms consistent with BTX effects. These symptoms have been reported hours to weeks after injection. Remote spread of toxin that affects swallowing and breathing can be life threatening, and there have been reports of death. The risk of symptoms is increased in subjects who have underlying conditions (e.g. disorders of the neuromuscular junction) that would predispose them to these symptoms.

Dysport® is contraindicated in individuals with known hypersensitivity to any BTX preparation or to any of the components in the formulation.

Adverse events of special interest (AESIs) for Dysport® are AEs that suggest a possible remote spread of effect of the toxin or hypersensitivity. A list of preferred terms of AESIs is provided in the Statistical Analysis Plan (SAP).

All AEs will be monitored by the sponsor to determine if they meet the criteria of AESIs. These AESIs will be further analysed to determine if there is a plausible possibility that they represent distant spread of toxin or hypersensitivity. In order to perform the analysis, variables including alternate aetiology (medical history, concomitant medication, or diagnosis which could account for the symptoms), location of Dysport® administration, and temporal relationship to Dysport® administration will be considered by the sponsor.

8.1.3 *Recording and Follow-up of Adverse Events*

At each visit, the subject should be asked a nonleading question such as: “How have you felt since starting the new treatment/the last assessment?”

All observed or volunteered AEs, regardless of treatment group or suspected causal relationship to IMP, will be recorded on the AE page(s) of the eCRF. Events involving drug reactions, accidents, illnesses with onset during the treatment phase of the study, or exacerbation of pre-existing illnesses should be recorded (see also [Section 8.1.2.7](#) and [Section 8.1.2.10](#)).

Any AEs already recorded and designated as “continuing” should be reviewed at each subsequent assessment.

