For all AEs, the investigator must pursue and obtain information adequate both to determine the outcome of the AE and to assess whether it meets the criteria for classification as a SAE requiring immediate notification to the sponsor or its designated representative. For all AEs, sufficient information should be obtained by the investigator to determine the causality of the AE (i.e. IMP or other illness). The investigator is required to assess causality and record that assessment on the eCRF. Follow-up of the AE, after the date of IMP discontinuation, is required if the AE or its sequelae persist. Follow-up is required until the event or its sequelae resolve or stabilise at a level acceptable to the investigator and the sponsor’s clinical monitor or his/her designated representative.

8.1.4 *Reporting of Serious Adverse Events*

All SAEs (as defined below) regardless of treatment group or suspected relationship to IMP must be reported immediately (within 24 hours of the investigator’s knowledge of the event) to the pharmacovigilance contact specified at the beginning of this protocol. If the immediate

report is submitted by telephone, this must be followed by detailed written reports using the SAE report form.

An SAE is any AE that:

- 1) Results in death
- 2) Is life threatening, that is any event that places the subject at immediate risk of death from the event as it occurred. It does not include an event that, had it occurred in a more severe form, might have caused death
- 3) Results in in-patient hospitalisation or prolongation of existing hospitalisation, excluding admission for social or administrative reasons (see further)
- 4) Results in a persistent or significant disability/incapacity, where disability is a substantial disruption of a person's ability to conduct normal life functions
- 5) Results in congenital anomaly/birth defect in the offspring of a subject who received the IMP
- 6) Is an important medical event that may not result in death, be life threatening, or require hospitalisation when, based upon appropriate medical judgement, may jeopardise the subject and may require medical or surgical intervention to prevent one of the outcomes listed in this definition. Examples of such medical events include allergic bronchospasm requiring intensive treatment in an emergency room or at home, blood dyscrasias or convulsions that do not result in in-patient hospitalisation, or the development of drug dependency or drug abuse.

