- any UTI TEAEs
 - UTI TEAEs leading to withdrawal
 - serious UTI TEAEs
- TEAE leading to death

In view of the anticipated difference in duration of the Dysport and placebo treatment cycles, this overview table will also be provided including only TEAEs occurring any time after first dose of IMP until up to 12 weeks after first IMP treatment administration.

A similar overview table will be produced for the number and percentage of subjects with at least one of the following events occurred pre-treatment for randomised subjects. The number of occurrences of the following events will be presented as well.

- any AE
 - Intensity of AE (mild, moderate, severe)
- any SAE
 - any SAEs leading to withdrawal
- AE leading to death

TEAEs will be summarised overall, for DPBC cycle, and Dysport Cycles with the number and percentage of subjects with TEAEs presented by primary SOC and PT. In addition, this table will be provided including only TEAEs occurring up to 12 weeks after first IMP treatment administration. This will also be summarised by aetiology of NDO.

The same summaries for overall, for DBPC Cycle, and Dysport Cycles with the number and percentage of subjects with TEAEs presented by primary SOC and PT will be presented for serious TEAEs, IMP-related TEAEs, TEAEs leading to withdrawal, TEAEs of special interest, and other protocol defined TEAEs. TEAEs with PTs observed in $\geq 1\%$, $\geq 2\%$, and $\geq 5\%$ of subjects and IMP-related TEAEs with PTs observed in $\geq 1\%$, $\geq 2\%$, and $\geq 5\%$ of subjects will be summarised as well.

Additionally, TEAEs will be tabulated by decreasing overall PT frequency and intensity in each SOC and PT category.

The above will also be presented for SAEs.

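### SAP 7.7.1 drops search-identified events from the AESI outputs when they cannot be assessed, so they are reported like events judged not to be AESIs

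*SAP*

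**What the plan says.** SAP 7.7.1 finds candidate AESIs in two ways: a preferred-term list for remote spread of toxin (Appendix VI) and a narrow standardised query for hypersensitivity. The sponsor reviews every candidate before database lock and unblinding, "to identify events which could possibly represent" remote spread or that suggest hypersensitivity.

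A candidate is excluded if another clinical cause accounts for it, if it is a local effect, if its timing does not fit the mechanism, "or due to insufficient information/evidence to make an assessment". The outputs are then restricted: "In the TFLs, only the final list of AESIs confirmed by the sponsor" counts.

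Protocol 8.1.2.11 gives the decision to the sponsor: "All AEs will be monitored by the sponsor to determine if they meet the criteria of AESIs". It describes the review by example: "In order to perform the analysis, variables including alternate aetiology", followed by injection location and temporal relationship. Protocol 9.4.7 makes AESI incidence a planned summary: "Incidence of all reported AEs/treatment emergent AEs, AESIs, and SAEs will be tabulated by treatment group".

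**The concern.** The first three exclusion grounds each rest on something known about the event that speaks against an AESI. The fourth rests on not knowing. When the question is whether an event might be remote spread or hypersensitivity, missing information does not answer no. The SAP nevertheless gives both kinds of case the same result: neither appears in any AESI output.

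What is at stake is how the AESI summary can be read. A reader of those tables sees the confirmed count. The visible text provides nothing that shows how many candidates the search flagged, or how many were set aside only because they could not be judged.

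**Working it through.** The plan gives no figure of its own to reproduce. The check compares the passages and then sizes one exclusion.

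**Step 1: grounds compared.**

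| SAP 7.7.1 exclusion ground | Counterpart in Protocol 8.1.2.11 | Nature of the ground |
|---|---|---|
| Alternative clinical cause | Alternate aetiology | Evidence against |
| Local effect, judged by injection site | Location of administration | Evidence against |
| Timing does not fit the mechanism | Temporal relationship | Evidence against |
| Not enough information to assess | None named | No evidence either way |

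Three of the four grounds map one-to-one. The fourth is added by the SAP.

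**Step 2: AESI outputs described in SAP 7.7.1.** There are three types:
- the AESI listing;
- the overview rows (by type of AESI, leading to withdrawal, serious);
- the summaries by system organ class and preferred term, which cover "serious TEAEs, IMP-related TEAEs, TEAEs leading to withdrawal, TEAEs of special interest, and other protocol defined TEAEs".

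None of the three (0 of 3) is described as separating a candidate judged not to be an AESI from one that could not be assessed.

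**Step 3: direction.** Incidence is the number of subjects with a confirmed AESI divided by the number in the analysis population for that cycle (SAP 7.1). Excluding an event can remove a subject from the numerator. It does not remove the subject from the safety population, so the denominator stays the same. Incidence can therefore only fall or stay unchanged.

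**Step 4: size per excluded subject with no other confirmed AESI.** Planned group sizes are from SAP 2.2 and Protocol 3.3.1.
- One arm in the placebo-controlled (DBPC) cycle: 110 for each Dysport dose; pooled placebo 55 + 55 = 110. 1/110 = 0.91 percentage points.
- All Dysport in the DBPC cycle: 110 + 110 = 220. 1/220 = 0.45 percentage points.
- Dysport Cycle 1 also takes in placebo subjects who later receive Dysport (SAP 7.1). That gives at most 110 + 55 = 165 per dose and 330 in all, so at least 1/165 = 0.61 and 1/330 = 0.30 percentage points.

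The total effect is the number of such subjects times these values. The documents do not give that number.

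**The case against.** The strongest reply is that a confirmed set is a legitimate thing to tabulate, and a case with too little information cannot be confirmed. The SAP states its rule openly and in advance, the protocol leaves analysis detail to the SAP, and safety analysis is descriptive, so no test depends on it. That stands as a reason to keep the confirmed tables as primary. It does not explain why the unassessable cases should go uncounted.

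Several limits also stand, and each rules out a stronger reading that a reader might infer.
- *The SAP contradicts the protocol.* It does not. The protocol's list of review variables is introduced as non-exhaustive, and the sponsor holds the decision.
- *The exclusion favours an arm.* Review is completed before unblinding, and nothing in the documents supports a claim of between-arm bias.
- *The events disappear.* They stay in the general TEAE tables and listings, and in the serious, related or withdrawal outputs where they qualify.
- *A zero in the AESI table cannot be interpreted.* That is too strong. TEAEs are tabulated by preferred term for the DBPC cycle and each Dysport Cycle, so a reader holding the search list can see whether flagged terms occurred. What stays hidden is why each one was not confirmed.
- *The loss can be scaled from the muscular-weakness rate in Protocol 1.3.2.* It cannot. Ten of those 14 cases followed 1000 U, above both trial doses; one symptom is not the whole flagged set; and Appendix VI is not visible.

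Protocol 8.1.3 also asks that "sufficient information should be obtained by the investigator to determine the causality of the AE", for every AE, which should keep unassessable cases few. Finally, the table shells, the redacted SAP section 11 and Appendix VI could not be checked and may contain a candidate-event display. The restriction to confirmed AESIs in 7.7.1 points against that but does not exclude it.

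**Conclusion.** The point holds as a transparency gap in a planned safety summary. SAP 7.7.1 states a rule under which an unassessable candidate is handled as a non-AESI. That sits poorly with a review framed around possibility, and the protocol does not name the ground. Its effect on AESI incidence is one-directional. At the planned DBPC sizes it is 0.91 points per affected subject in an arm and 0.45 for All Dysport; if fewer subjects are treated, each value rises slightly. How many subjects are affected is unknown and probably small. The conclusion rests on the visible text of SAP 7.7.1 and Protocol 8.1.2.11, and on the shells not already supplying the missing display. It does not call any efficacy or safety conclusion invalid.

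**What to change.** - Keep the sponsor-confirmed AESI tables as the primary AESI summary.
- In SAP 7.7.1, replace the insufficient-information exclusion with a review outcome of not assessable.
- Add two rows to the AESI overview, by treatment group and cycle: all search-identified (potential) AESIs, and those not assessable.
- Add a listing of every flagged TEAE with its review outcome and, where it was not confirmed, the reason.
- Align the wording of SAP 7.7.1 and Protocol 8.1.2.11 on how unassessable events are handled.

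If the table shells already contain these outputs, a cross-reference in 7.7.1 is enough.

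The cost is two table rows and one listing, built from events that are already coded and reviewed before lock. The drawback is that a higher, less specific count will appear beside the confirmed one, so the rows need clear labels.
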